Recent phase II trials have shown that intravenous tenecteplase is potentially safer and may achieve higher early reperfusion rates than alteplase in patients with acute ischemic stroke. Bolus administration makes tenecteplase easier to administer than alteplase (which requires infusion pumps). Transfer of patients from primary stroke centers (PSC) to comprehensive stroke centers (CSCs) is potentially easier without infusion pumps. Moreover, depending on the province, tenecteplase either costs the same, or even less, than alteplase. It is therefore possible that the use of intravenous tenecteplase in patients with acute ischemic stroke otherwise eligible for intravenous alteplase may result in faster administration of thrombolysis and more efficient transport to CSCs, thus saving time, reducing adverse events (intracranial hemorrhage) and potentially improving patient outcomes, while saving the health system costs. For these various reasons, robust evidence that tenecteplase is non-inferior to alteplase as an intravenous thrombolytic agent in patients with acute ischemic stroke will change current clinical practice as it did in patients with myocardial infarction.

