#### 5.2 Planned trial interventions

The intervention group will receive intravenous tenecteplase as a single bolus at a dose of 0.25 mg/kg body weight (maximum dose 25 mg) as soon as possible after randomization.

The control group will receive standard of care dosing of intravenous alteplase (0.9 mg/kg body weight, 10% bolus and 90% infusion as per standard care, maximum dose 90 mg).

All patients will have standard of care medical management on an acute stroke unit. There are no additional trial specific management recommendations.

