#### 5.9 Primary and secondary outcome measures

#### Primary Outcome: modified Rankin Scale 0-1 at 90 - 120 days

#### **Secondary Outcomes:**

- 1. Discharge destination (home, early supported discharge, rehabilitation facility, long term care, death) \* #
- 2. Home time (defined as number of days subject spends at home after index stroke event) 
- 3. Actual 90-120 day mRS score\*#
- 4. Door to needle time\*#
- 5. Door-in-door-out (DIDO) times at Primary Stroke Centres\*#
- 6. Recanalization status (mTICI score) at first angiographic acquisition in patients taken to the angio-suite for the purpose of administering EVT\*#
- 7. Proportion of patients administered EVT \*#
- 8. Door-to-groin puncture time in patients undergoing EVT\*#
- 9. CT-to-puncture time in patients undergoing EVT\*#
- 10. Return to baseline level of functioning
- 11. Cognition assessed via a brief, on-line cognitive assessment tool.

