#### 6.6 Proposed types of analyses

Primary efficacy analysis will be intention to treat. Given pragmatic eligibility criteria and up-front one-time treatment, we expect no cross-overs and very few protocol violations. A protected hierarchical analysis plan will be performed. First, non-inferiority will be established if the lower boundary of the 95% confidence interval of the % difference in subjects achieving good outcome (mRS 0-1) in the tenecteplase versus the alteplase arm is greater than -5% (the non-inferiority margin). If non-inferiority is demonstrated, then a test of superiority will be performed as part of secondary analysis. The primary analysis for efficacy will be a stratified Cochran-Mantel-Haenszel (CMH) test where registry (QuICR vs. OPTIMISE) will be used as a stratification variable. If noninferiority is not demonstrated, all subsequent analyses will be considered hypothesis-generating. As sensitivity analysis, logistic regression will be used to provide an adjusted estimate of effect size of the effectiveness of tenecteplase over alteplase. The odds ratio of good 90-day outcome associated with the treatment groups will be estimated using a logistic regression model after adjusting for registry, age, sex, baseline stroke severity and onset-to-needle time. For secondary analyses, frequency tables will be used to summarize binary variables by treatment group. Descriptive statistics will be used to summarize continuous data variables by treatment group. Similar to the primary efficacy variable, binary secondary outcomes will be analyzed using logistic regression analysis. The continuous secondary outcomes will be analyzed using analysis of covariance (ANCOVA) and mixed-effects regression with the registry (QuICR vs. OPTIMISE) variable treated as a randomeffect. If non-inferiority of the primary outcome is demonstrated, a hierarchical multiplicity

adjustment will be used to determine the Type I error for testing the secondary outcomes in order to control the overall familywise type I error rate for the study. Sex will be a unit of analysis. In addition, given previous literature suggesting underutilization of thrombolysis in females, sex-based differences in recruitment, workflow and processes and outcomes will constitute important prespecified subgroup analyses. Details will be provided in the statistical analysis plan that will be developed and reviewed by the trial steering committee.

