## 9. Statistical Analysis

Primary analysis of the trial data to establish non-inferiority will be conducted using risk difference analysis. First, non-inferiority will be established if the lower boundary of the 95% confidence interval of the percentage difference in subjects achieving excellent outcome (mRS 0-1) in the tenecteplase versus the alteplase arm is greater than – 5% (the non-inferiority margin). If non-inferiority is demonstrated, then a test of superiority of tenecteplase vs. alteplase will be performed as part of secondary analysis. In addition, logistic regression will be used to provide an adjusted estimate of the effectiveness of tenecteplase over alteplase for the primary outcome. The risk ratio of good 90-day outcome (mRS01) associated with the treatment groups will be estimated using a mixed-effects logistic regression model that adjusts for age, sex, baseline stroke severity, and stroke onset-to-needle time as fixed effects, and site, and registry (QuiCR vs. OPTIMISE) as random effects.

Secondary analyses will evaluate key safety (mortality and symptomatic intracerebral hemorrhage as defined in the AcT trial MOP) and secondary outcomes using relevant tests of association. Frequency tables will be used to summarize categorical variables by treatment group. Descriptive statistics will be used to summarize continuous data variables by treatment group.

The secondary outcomes and the corresponding analyses are described as follows. Both unadjusted (not described in Table below) and adjusted (described in table below) will be reported. Unadjusted analysis will be tests of difference in proportions, means or medians or regression analysis as appropriate. All analyses will be conducted secondary analyses are conducted at  $\alpha$  = 0.05.

Outcome	Analysis
mRS 0-1 i.e., excellent	Efficacy secondary analysis of the mRS 0-1.
functional outcome (blinded)	Logistic mixed-effects regression model with
	treatment (Tenecteplase vs Alteplase) as
	exposure; age, sex, baseline stroke severity, and
	stroke onset-to-needle time as fixed effects, and
	site, and registry (QuiCR vs. OPTIMISE) as random
	effects.
mRS 0-2 i.e., good functional	Risk difference and the corresponding 95%CI to
outcome (blinded)	assess non-inferiority. Risk ratio and the 95%CI to
	evaluate efficacy

Page 5 of 9

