	Adjusted logistic mixed-effects regression model with treatment (Tenecteplase vs Alteplase) as exposure; age, sex, baseline stroke severity, and stroke onset-to-needle time as fixed effects, and site, and registry (QuiCR vs. OPTIMISE) as random effects.
Ordinal mRS (blinded)	Ordinal logistic mixed-effects regression with treatment (Tenecteplase vs Alteplase) as exposure; for age, sex, baseline stroke severity, and stroke onset-to-needle time as fixed effects, and site, and registry (QuiCR vs. OPTIMISE) as random effects.
Return to pre-stroke status (pragmatic outcome) (blinded)	Risk difference and the corresponding 95%CI to assess non-inferiority. Risk ratio and the 95%CI to evaluate efficacy
	Adjusted logistic regression analysis with treatment (Tenecteplase vs Alteplase) as exposure; age, sex, baseline stroke severity, and stroke onset-to-needle time as fixed effects, and site, and registry (QuiCR vs. OPTIMISE) as random effects.
Euroqol 5-D Visual Analogue Scale (EQ5D-VAS) (blinded)	A linear mixed-effects regression model with treatment (Tenecteplase vs Alteplase) as exposure; age, sex, baseline stroke severity, and stroke onset-to-needle time as fixed effects, and site, and registry (QuiCR vs. OPTIMISE) as random effects.
EQ5D-5L (blinded)	Adjusted and unadjusted ordinal logistic regression analyses will be conducted for each EQ5D item (mobility, self-care, usual activities, anxiety, and depression) as the outcome variable.
	Health utility index derived from the EQ5D-5L items.
	Linear regression analysis with robust standard errors with treatment (Tenecteplase vs Alteplase) as exposure; age, sex, baseline stroke severity, and stroke onset-to-needle time as fixed effects,

Page 6 of 9

	Q
	and site, and registry (QuiCR vs. OPTIMISE) as
	explanatory variables.
Home time*	A generalized linear mixed-effects regression model with treatment (Tenecteplase vs Alteplase) as exposure; age, sex, baseline stroke severity, and stroke onset-to-needle time as fixed effects, and site, and registry (QuiCR vs. OPTIMISE) as random effects.
	In addition to home time, similar exploratory analysis will be conducted for other registry and administrative data outcomes such as length of hospital stay until discharge and discharge destination (home, home with home care, home with early supportive discharge, rehabilitation hospital, long term care and hospice) that will use appropriate regression analysis.
Mortality	Risk difference and the corresponding 95%CI

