	A Kaplan-Meier survival distribution. Patients alive after 90/120 days were censored. Logistic mixed-effects regression model with treatment (Tenecteplase vs Alteplase) as exposure; age, sex, baseline stroke severity, and stroke onset-to-needle time as fixed effects, and site, and registry (QuiCR vs. OPTIMISE) as random effects.
Symptomatic intracerebral hemorrhage	Risk difference and the corresponding 95%CI
	Logistic mixed-effects regression model with
	treatment (Tenecteplase vs Alteplase) as
	exposure; age, sex, baseline stroke severity, and
	stroke onset-to-needle time as fixed effects, and site, and registry (QuiCR vs. OPTIMISE) as random effects.
Intracranial Hemorrhage on follow-up Imaging (Blinded)	Difference in proportion of ICH categories and the corresponding 95%Cl

Page **7** of **9** 

 
Parenchymal hemorrhage (hemorrhagic infarction type 1, hemorrhagic infarction type 2, parenchymal hematoma type 1, parenchymal hematoma type 2, remote hemorrhagic infarction type 1, remote hemorrhagic infarction type 2, remote parenchymal hematoma type 1, remote parenchymal hematoma type 1, remote parenchymal hematoma type 2)
 
Subdural hemorrhage
 
Subarachnoid hemorrhage
 
Intraventricular
 
	
Peripheral Bleeding requiring Blood Transfusion	Risk difference and the corresponding 95%CI
Angioedema	Risk difference and the corresponding 95%Cl
Proportion of patients receiving EVT	Risk difference and the corresponding 95%CI.
	Logistic mixed-effects regression model with
	treatment (Tenecteplase vs Alteplase) as
	exposure; age, sex, baseline stroke severity, and
	stroke onset-to-needle time as fixed effects, and site, and registry (QuiCR vs. OPTIMISE) as random effects.
Other SAEs and SUSARs	Risk difference and the corresponding 95%CI

Page **8** of **9** 

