#### **10. Subgroup Analyses**

Heterogeneity in treatment effects will be explored via subgroup analyses of pre-specified prognostic variables in the ITT population primarily and in the per-protocol population secondarily. These will include analysis of primary outcome (mRS01) and key safety outcomes by

- a. age (continuous and as < 80 years vs. >= 80 years),
- b. sex (male vs. female),
- baseline stroke severity as measured by the National Institute of Health Stroke Scale (NIHSS; continuous and < 8, 8-15 vs > 15),
- d. presence of large vessel occlusion on baseline CTA
- e. stroke onset-to-needle time (continuous and as <=180 minutes vs. > 180 minutes)
- f. registry (QuiCR vs. OPTIMISE),
- g. type of enrolling hospital (PSCs vs. CSCs),

Evidence of a treatment-by-sub-group variable interaction will be tested by including a multiplicative interaction term (treatment\*subgroup variable) in the model. Subgroup analyses will help to determine if there is efficacy or futility in any pre-specified subgroup. Statistical significance for each subgroup analysis will be exploratory and conducted at  $\alpha = 0.05$ 

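### The adjusted models that list their covariates, and one subgroup, use onset-to-needle time, which ends after open-label randomisation and which tenecteplase may shorten

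*Combined protocol and SAP*

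**What the plan says.** SAP section 9 supplements the primary risk difference with a logistic model for mRS 0-1 that "adjusts for age, sex, baseline stroke severity, and stroke onset-to-needle time as fixed effects", with site and registry as random effects. The outcome table repeats the set "age, sex, baseline stroke severity, and stroke onset-to-needle time as fixed effects" for mRS 0-1, mRS 0-2, ordinal mRS, return to pre-stroke status, EQ5D-VAS, the EQ-5D utility index, home time, mortality, symptomatic ICH and receipt of EVT. Protocol section 6.6 specifies a sensitivity logistic regression "adjusting for registry, age, sex, baseline stroke severity and onset-to-needle time". SAP section 10, item e, makes a subgroup of "stroke onset-to-needle time (continuous and as <=180 minutes vs. > 180 minutes".

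On timing, protocol section 5.2 has tenecteplase given "as soon as possible after randomization". Section 5.3 has the randomiser return the allocation together with the calculated dose, and SAP section 8 confirms that treatment is open label. Section 4.1 says tenecteplase "may result in faster administration of thrombolysis", and section 5.9 lists "Door to needle time" as a secondary outcome.

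**The concern.** A covariate in a randomised comparison should be fixed before allocation. The last segment of onset-to-needle time, from randomisation to injection, is not. The team prepares the drug knowing which one it is, and protocol section 4.3.2 names dose calculation and pump set-up as sources of delay with alteplase. Section 4.6 goes further and suggests that shorter workflow times could improve outcomes. On that argument, time to needle lies on the path from assignment to outcome: the plan would study it as a possible effect of treatment and also hold it constant.

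Three things are at stake:

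- The adjusted estimates could omit whatever part of the effect runs through speed, and could be distorted by unmeasured causes of delay that also affect outcome.
- Patients randomised but never treated have no value for the covariate and would leave models that the SAP presents under intention to treat.
- A patient near 180 minutes could fall into one subgroup or the other because of the allocated drug.

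**Working it through.** **Which analyses are affected.** Ten SAP outcome models list covariates, and all ten include onset-to-needle time. Protocol section 6.6 and subgroup e make two further uses. There are exceptions. For the EQ-5D items the SAP says only that "Adjusted and unadjusted ordinal logistic regression analyses will be conducted for each EQ5D item", without naming covariates, and the length-of-stay and discharge-destination analyses are described only in general terms.

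**What is not affected.** The plan's sample size uses planned rates alone. With 35% and 38%, a 5-point margin, one-sided 2.5% and 90% power:

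n per arm = (1.95996 + 1.28155)² × (0.35×0.65 + 0.38×0.62) / (0.03 + 0.05)² = 10.507 × 0.4631 / 0.0064 = 760.3, so 761, against 759 stated. Then 2×759 / 0.95 = 1598, against 1600 stated.

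The figure reproduces closely and involves no covariate. The primary test is an unadjusted risk difference in SAP section 9, or a registry-stratified CMH test in protocol section 6.6. Neither uses needle time.

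**Size on mRS 0-1 from the protocol's own figures.** Inputs:

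- alteplase effect of 10 points, so NNT 10 (protocol section 6.1);
- NNT rising by 1 per 20 minutes of delay (protocol section 4.3.1);
- assumed shortening of time to needle, d minutes, because the documents give no figure.

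Part of the effect carried by speed, and so removed by the adjustment = 1/10 − 1/(10 + d/20). For d = 5: 0.1000 − 1/10.25 = 0.0024. For d = 10: 0.1000 − 1/10.5 = 0.0048.

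| d (min) | Points removed | Share of assumed 3-point benefit | Share of 5-point margin | Simulation (points) |
|---|---|---|---|---|
| 0 | 0 | 0% | 0% | about 0 |
| 2 | 0.10 | 3% | 2% | 0.1 |
| 5 | 0.24 | 8% | 5% | 0.2-0.3 |
| 10 | 0.48 | 16% | 10% | 0.4-0.5 |
| 15 | 0.70 | 23% | 14% | 0.6 |
| 20 | 0.91 | 30% | 18% | not run |

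The last column comes from logistic models fitted to 2,000,000 simulated patients per scenario. It assumes a mean of 15 minutes from randomisation to needle and a median of 110 minutes from onset to randomisation, with or without an unmeasured common cause of delay and poor outcome. Its time slope was set from the same gradient, so it checks the mechanism and is not independent evidence of size. With d = 10 and no common cause, the standardised risk difference was 3.45 points unadjusted, 3.01 adjusted for onset-to-needle time and 3.45 adjusted for onset-to-randomisation time. In every scenario the last agreed with the unadjusted figure to within 0.01 points.

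**Scale.** At 800 per arm the 95% interval half-width for the primary risk difference is 1.96 × √(0.4631/800) = 0.047, or 4.7 points. The shift is small beside that.

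**Safety.** The documents give no time gradient for death or symptomatic ICH, so no corresponding figure can be produced.

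**Untreated patients.** SAP section 7.2 requires receipt of some study drug for the per-protocol set, so the plan allows for randomised patients without it. SAP section 11 keeps all randomised patients in the analysis apart from those with missing mRS through refused consent. A complete-case model with needle time as a covariate cannot do that. The documents give no expected number of such patients.

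**The case against.** The strongest reply is that little depends on these models. The non-inferiority decision does not use them, and protocol section 6.6 labels its version a sensitivity analysis. The SAP also promises unadjusted results for the secondary outcomes, with risk differences alongside the adjusted models for mRS 0-2, return to pre-stroke status, death, symptomatic ICH and EVT. That stands, and it limits the severity.

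It is also fair that most of the interval is legitimate baseline information, that protocol section 6.3 describes treatment as following randomisation at once, that few protocol violations are expected, and that the subgroups are exploratory. A short gap leaves little room for an arm difference, although no duration is stated.

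A reader might infer more than the documents support:

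- *That every adjusted analysis is biased.* Some models name no covariates, and the problem arises only if time to needle differs by arm. The protocol's language on speed is tentative.
- *That non-inferiority could be manufactured.* The primary test does not use the covariate, and in the adjusted mRS 0-1 model the loss runs against tenecteplase if it is faster.
- *That the safety estimates are biased in a known direction.* Nothing in the documents allows that to be worked out.

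None of this gives a reason to prefer onset-to-needle time as the covariate.

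**Conclusion.** The point holds at moderate severity. If tenecteplase changes time to needle, the adjusted estimates answer a different question from the effect of assignment. For a 5-10 minute shortening the difference on mRS 0-1 is about 0.24-0.48 points, and it stays below 1 point up to 20 minutes. This rests on a starting NNT of 10, on the alteplase delay gradient applying to this population, outcome and both drugs, and on an assumed time difference. With equal needle times it is zero. For death and symptomatic ICH the size and sign are unknown. The loss of untreated patients and the movement of patients across the 180-minute cut are real in principle but cannot be sized from the documents.

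**What to change.** In protocol section 6.6, in each SAP section 9 model that lists covariates, and in SAP section 10 item e, replace onset-to-needle time with onset-to-randomisation time. State the covariates of the EQ-5D item models at the same time. Keep needle-time measures as outcomes. If adjustment for onset-to-needle time is still wanted, report it only as a labelled sensitivity analysis and say that it does not estimate the total effect of assignment.

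The cost is mainly wording. Onset time is already needed. The real-time server in protocol section 5.3 implies a randomisation time stamp, but the documents do not list one as an analysis field, so this should be confirmed. Onset-to-door time is the fallback, since door time is needed for door-to-needle time. The one trade-off is that the 180-minute cut would then refer to randomisation (or arrival), so the subgroup would no longer match time-to-treatment strata exactly. Sample size and the primary test do not change.

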#### 5.3 Proposed practical arrangements for allocating participants to trial groups

Eligible patients will be randomized in a 1:1 ratio. Randomization will use a validated minimal sufficient balance (MSB) algorithm, to assure balance by site. The algorithm will kick in after the site has enrolled 5 subjects. The standard distribution is 50-50, but when an imbalance is detected with a p-value less than 0.3, the distribution changes to 65-35 in the direction against the imbalance. Randomization will be centralized, secure and concealed using a real-time web-based server, thus eliminating the possibility of confounding due to allocation bias. The central server will be linked to a randomization mechanism and will only be able to allocate one patient to either arm of the trial at one time. Investigators will be able to rapidly access the randomizer through a secure internet web browser or secure automated phone number or text message. Investigators will have to enter a site-specific ID number followed by an Investigator specific ID number and the weight of the patient in kilograms. They will then receive the drug allocation (tenecteplase vs. alteplase) along with unique study subject ID and the calculated drug dosage. They will later be prompted to enter if a) the correct drug was administered b) the correct dose was administered and c) the vial LOT number and expiry date of the administered drug.

Emails will be sent from the central trial server to site investigators and trial personnel with the site ID, unique study subject ID and drug allocation (study enrolment form). A copy of this email can be

printed and included in the patient chart. In addition, this email will also have a PDF checklist reminding site co-ordinators to ensure the following

- 1. The study enrolment form is placed in the clinical patient chart
- 2. The patient and surrogate contact information is documented in the checklist
- 3. Consent is obtained (see section 5.4) and documented in the study database
- 4. The unique study subject ID and registry ID are entered in the study database
- 5. Report any serious adverse events occurring within the first 24 hours of randomization. This information will be documented on paper and/or in the study database

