## 7. Definition of the target populations

7.1. Intention to Treat population All patients enrolled in the trial randomized on an intent-to-treat basis.

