7.2. Per-protocol population

All patients enrolled in the trial who received any dose of study drug and met all the inclusion and exclusion criteria per current Canadian Stroke Best Practices Recommendations. Since the trial has pragmatic eligibility criteria, patients who may have been inadvertently enrolled and received thrombolysis beyond 4.5 hours from stroke onset and any treatment crossovers are defined as protocol deviations for analysis.

Page 4 of 9

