#### 11. Missing data

Since the trial enrolls participants using a deferred consent approach, participants with missing mRS because of refusal of consent will be excluded completely from the analysis. Under the ITT principle, all remaining patients who are randomized are included in the analysis. Thus, every effort will be made to keep all missing data to a minimum i.e., < 5%. If, despite best efforts, there are missing data, then for the primary outcome analysis, data will be assumed to be missing completely at random (MCAR). Sensitivity analyses will be conducted to examine the impact of MCAR assumption on study conclusions using available case analysis and multiple imputation methods. Similarly, assumptions and missing data methods will be adopted for analysis of secondary outcomes.

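### The SAP names no population for the safety outcomes and defines no as-treated safety set, so by default drug harms would be counted by arm assigned

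*Combined protocol and SAP*

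**What the plan says.** SAP 7 defines two populations. The first is ITT: "All patients enrolled in the trial randomized on an intent-to-treat basis". The second is per-protocol (SAP 7.2): "All patients enrolled in the trial who received any dose of study drug and met all the inclusion and exclusion criteria", judged against Canadian best-practice recommendations. SAP 7.2 adds that "any treatment crossovers are defined as protocol deviations for analysis", as is thrombolysis given beyond 4.5 hours. It does not say that a crossed-over patient is regrouped under the drug received. There is no safety or as-treated population.

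SAP 9 introduces the safety outcomes together with the other secondary outcomes: "Secondary analyses will evaluate key safety (mortality and symptomatic intracerebral hemorrhage as defined in the AcT trial MOP) and secondary outcomes using relevant tests of" … The table rows for mortality, symptomatic ICH, haemorrhage on imaging, bleeding requiring transfusion, angioedema and other SAEs give the analysis method but no population. Summaries are by treatment group, which is not defined as assigned or received.

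Two other sections point to ITT. SAP 11 first removes patients whose mRS is missing because consent was refused, and continues: "Under the ITT principle, all remaining patients who are randomized are included in the analysis". SAP 10 places the subgroup analyses, which include key safety outcomes, "in the ITT population primarily and in the per-protocol population secondarily".

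The drug actually given is recorded. Protocol 5.3 says of the investigators: "They will later be prompted to enter if a) the correct drug was administered b) the correct dose was administered". Protocol 7.4, item 4, repeats this.

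**The concern.** Symptomatic ICH, bleeding and angioedema are effects of the drug that entered the patient. If they are tabulated by arm assigned, a patient randomised to tenecteplase who was given alteplase and bled counts as a tenecteplase bleed. A patient who was randomised and never thrombolysed counts as exposed and event-free. For a claim that one drug is no more harmful than another, dilution of this kind is not conservative.

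The trial has a safety argument to make. Protocol 4.1 and 4.6 give fewer haemorrhages and possibly better safety as reasons to change practice, and protocol 5.11 judges events in the first 24 hours by their relation to either agent. Attribution to an agent needs the agent received. The trial is open label, so leaving the safety population unstated also leaves room to choose it after results by arm are known.

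**Working it through.** **1. Figures in the plan.** The documents give no crossover rate, no non-treatment rate and no power statement for safety. The only plan figure needed is the arm size. The stated 759 per arm is reproduced closely (761 with 35% against 38%, margin 5 points, one-sided alpha 2.5%, power 90%). Allowing for 5% loss, 759 / 0.95 = 799 per arm, or 1,598 in all, rounded to 1,600. So there are 800 randomised per arm.

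**2. Dilution with equal rates in both arms.** Let pT and pA be the event risks on tenecteplase and alteplase, p0 the risk if untreated, c the fraction crossing over and u the fraction untreated, with c and u the same in each arm.

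- Tenecteplase arm as assigned: (1 − c − u)pT + c·pA + u·p0
- Alteplase arm as assigned: (1 − c − u)pA + c·pT + u·p0
- Difference: (1 − u − 2c)(pT − pA)

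The term in p0 cancels, so no assumption about its size is needed, only that it is the same in both arms. With assumed rates:

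- u = 0.5%, c = 0.25%: 1 − 0.005 − 0.005 = 0.99
- u = 2%, c = 1%: 1 − 0.02 − 0.02 = 0.96
- u = 3%, c = 2%: 1 − 0.03 − 0.04 = 0.93
- u = 5%, c = 5% (a stress case): 1 − 0.05 − 0.10 = 0.85
- u = c = 0: 1, no dilution

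**3. What this does to symptomatic ICH.** Take the 3.2% for alteplase from protocol 4.5.1 and an assumed doubling to 6.4% on tenecteplase, with 800 per arm, two-sided alpha 0.05 and an assumed 1% risk if untreated (needed for the power). The true difference is 3.20 points and the power 85.0%. At u = 2%, c = 1% the difference is 0.96 × 3.20 = 3.07 points and the power 82.6%. In the stress case it is 0.85 × 3.20 = 2.72 points and the power 73.7%. At the protocol's own 3.3% against 3.2%, the difference is 0.1 point either way.

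**4. Unequal non-treatment.** Assume symptomatic ICH of 5.0% on tenecteplase, 3.2% on alteplase and 1% untreated. The true difference is 1.80 points.

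- 5% untreated in the alteplase arm only: 5.0 − (0.95 × 3.2 + 0.05 × 1.0) = 5.0 − 3.09 = 1.91 points
- 5% untreated in the tenecteplase arm only: (0.95 × 5.0 + 0.05 × 1.0) − 3.2 = 4.80 − 3.2 = 1.60 points

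The direction is therefore not fixed.

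**5. Rare reactions.** Protocol 4.4 gives about 1% severe angioedema, for alteplase-treated patients. In 800 that is 8 events, so one misattributed event changes the arm's rate by 1/8 = 12.5%. At the NOR-TEST day-7 counts in protocol 5.11 (1/549 and 2/551), 800 patients would give about 1.5 and 2.9 events, and one misattribution could reverse the comparison. It is unlikely to occur often: with 8 events and c = 1%, about 0.08 events per arm are expected to be misattributed.

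**6. Whether the existing sets already cover this.** The per-protocol set requires receipt of some drug, but also that all eligibility criteria are met, so it removes patients who were exposed and were found ineligible. It does not group patients by drug received. SAP 10 uses it for safety only in second place, within subgroups. The adjusted models for mortality and symptomatic ICH include onset-to-needle time, which an untreated patient does not have. Such patients would probably drop out of the adjusted models but stay in the unadjusted risk differences, so the two results for one outcome could rest on different patients.

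**The case against.** The strongest reply is that the effect is small and hypothetical. Protocol 6.6 expects no crossovers and very few violations in a one-dose treatment given straight after randomisation. At 3.2% symptomatic ICH and 800 per arm, the 95% confidence interval for the difference is about ±1.7 points, whereas a 4% dilution of a true 1-point difference is 0.04 points. ITT also preserves the randomised comparison, and a pragmatic trial can defend it as primary for safety. All of this stands. It limits the severity and is a reason to keep ITT in the report.

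Four stronger readings are tempting, and the documents do not support them.

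- A reader might infer that the SAP prescribes ITT for the main safety tables. It does not: SAP 9 names no population, and protocol 6.6 ties intention to treat to primary efficacy. ITT is the default reading from SAP 10 and 11.
- A reader might infer that every randomised patient is counted. SAP 11 excludes those whose mRS is missing because consent was refused.
- A reader might infer that the record of drug given is never used for safety. The per-protocol set depends on it, and SAP 10 applies that set to key safety outcomes, though only secondarily and in subgroups.
- A reader might infer that the bias always runs towards no difference. That holds for crossovers and for equal non-treatment; step 4 shows that unequal non-treatment can go either way.

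**Conclusion.** The gap is real: no population is stated for the safety outcomes, and no population groups patients by the drug they received. Under the default reading, a true harm difference would shrink by 1% to 7% over the assumed ranges of u and c, and by 15% in the stress case. These sizes assume equal rates in both arms, the same risk in untreated patients of either arm, and crossed-over patients who carry the risk of the drug received. With no crossovers and no untreated patients the effect is nil. Correct attribution of rare reactions, and having one defined set of patients behind each safety result, are better reasons to act than the dilution. This is a cheap improvement of low severity; it does not touch the primary non-inferiority conclusion.

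**What to change.** Add a third population to SAP 7: a safety population of all patients who received any dose of tenecteplase or alteplase, grouped by the drug actually received. In SAP 9, name the population for each safety row. Report symptomatic ICH, haemorrhage on imaging, bleeding requiring transfusion, angioedema and other SAEs/SUSARs in the safety population alongside the ITT results. Keep mortality primarily on ITT, in line with SAP 6, which compares mortality between the randomised groups at the interim looks. Report by arm the numbers untreated and crossed over, so that the reader can judge how far the two analyses could differ.

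The cost is a few lines of SAP text and one extra set of tables from data already captured under protocol 5.3 and 7.4. The downside is that the as-treated comparison is not strictly randomised, which is why ITT stays beside it.
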